We designed a four-week early OT intervention program for patients who have suffered a stroke with the aim of improving quality of life and facilitating their return home by providing them and their caregiver with knowledge about specific care and neurorehabilitation.

Specific Objectives

Primary outcome: Quality of life. Secondary results: Functional independence and support needs in activities of daily living, sensory-motor skills, perceptual-cognitive skills, communication skills, anxiety and depression levels.

Methods

Type and general design of the study

This is a prospective, randomized, controlled clinical trial. The population to be represented is that of patients who are discharged from the neurology service of the Virgen de la Victoria University Hospital (Malaga) and who, after medical discharge, are referred to the rehabilitation service of the Maritime Hospital of Torremolinos as outpatients by decision of the neurology and rehabilitation departments, but will not be inpatients in the Physical Medicine and Rehabilitation Unit for intensive rehabilitation.

Users who are referred to rehabilitation by obtaining a place as an inpatient, receive occupational therapy and physiotherapy daily for a period of maximum three months. However, patients who are referred to the rehabilitation service as an outpatient are taken home directly after discharge and are subsequently recalled for rehabilitation. The period that elapses from when they are discharged until they are called to begin their rehabilitation varies depending on the workload of the service, and can even be three months after discharge. Referral to external or intensive rehabilitation is made based on the rehabilitation potential, which takes into account certain criteria such as age, clinical situation and vascular injury existing at the time of discharge, social support, motivation and observed recovery. during admission. Patients assigned to the study program are included in an early occupational therapy intervention program and are compared with a control group that will receive usual care and rehabilitation.

Sample selection and size

The sample size "n" was calculated based on the main variable SAQOL-39 with the sample size determination formula for two independent groups, assuming a mean of 2.50, standard deviation of 0.75, significance level of 5%, a power of 80% and a critical difference of 0.54, obtaining a sample of 30 participants per group.

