- Stroke and Aphasia Quality of Life Scale 39, SAQOL-39 (Lata-Caneda, Piñeiro- Temprano, García-Fraga, García- Armesto, Barrueco-Egido, Meijide-Failde, 2009). SAQOL-39 was derived from the Stroke-Specific Quality of Life Scale and four additional items specifically targeting patients with aphasia, covering four domains: physical, psychosocial, communication, and energy.
- Montreal Cognitive Assessment, MoCA (Lozano Gallego, Hernández Ferrándiz, Turró Garriga, Pericot Nierga, López- Pousa, Vilalta Franch, 2009). MoCA has been proposed as a screening tool that promises good sensitivity to deficits resulting from stroke and vascular cognitive impairment. MoCA includes sections on visuospatial/executive functions, naming, attention, language, abstraction,

memory, and orientation. It is scored out of 30 (extra point for <13 years of education) and the recommended "normal" limit is ≥26.

- *Modified Rankin Scale*, *mRS* (Van Swieten, Kodustaal, Visser, Schouten, Van Gijn, 1988). The mRS is used to describe disability in general. The scale ranges from 0 to 6, from perfect health with no symptoms to death.
- Fugl-Meyer sensory motor assessment, FMA (Ferrer González, Zarco Periñán, Ruiz de Vargas, Docobo Durantez, 2015). It evaluates the upper extremity (maximum score of 66 which corresponds to normal motor function) and lower extremity (maximum score of 34). Tenderness, passive range of motion, and pain during passive joint movements are also evaluated.
- Timed up and go, TUG (Hafsteinsdóttiret al, 2014). TUG assesses basic mobility, timing the time required for a person to stand up from a standardized chair, walk a distance of three meters, turn, return to the chair, and sit down again. A shorter time indicates better performance. It has been shown to be reliable and valid in this group of patients.
- Berg Balance Scale, BBS (Kudlac, Sabol, Kaiser, Kane, Phillips, 2019). BBS assesses functional balance. Performance on this test is scored from 0 (unable to perform) to 4 (normal performance) on 14 different tasks, including the ability to sit, stand, reach, bend, turn, and step. The maximum score on the BBS is 56. A higher score indicates better balance skills.

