- Barthel Index, BI (Baztán, Pérez del Molino, Alarcón, San Cristobal, Izquierdo, Manzarbeitia, 1993). The Barthel Index measures the extent to which someone can function independently during basic activities of daily living (ADLs), i.e., feeding, bathing, grooming, dressing, bowel control, bladder control, grooming, chair transfers, ambulation and climbing stairs. Each performance element is rated on this scale with a given number of points assigned to each level. In this study, the modified version with 0–100 is used, where a lower score indicates dependence.
- Stroke Impact Scale 16, SIS-16 (Duncan, Lai, Bode, Perera, DeRosa, 2003). The usefulness of this scale is similar to that of the Barthel Index, although it is more sensitive than the latter for discriminating between patients with mild disabilities. It is designed especially for patients who have suffered a stroke, but it is also applicable to dementia. It is a reduced version of the Stroke Impact Scale version 3.0. The information can be obtained from the patient himself, or from the main caregiver (15) (16).
- Communicative Activity Log, CAL (Pulvermüller & Berthier, 2008). Scale that allows obtaining information on the communication capacity in the activities of daily life referring to comprehensive and expressive aspects of language. It is composed of 36 items (Likert-type scale, 0-6) that evaluate both the quality (items 1-18) and the quantity of patient communication (items 19-36). Performance is obtained through the sum of the scores on each item.

- Beck Depression Inventory, BDI-2 (Steer, Brown, 1996). It is a self-administered questionnaire that consists of 21 multiple-choice questions. It is one of the most commonly used instruments to measure the severity of depression.
- Hamilton Anxiety Scale (Lobo et al, 2002). This scale evaluates the severity of anxiety globally in patients who meet criteria for anxiety or depression. In addition, this instrument is useful to monitor the response to treatment. It is composed of 14 items, 13 referring to anxious signs and symptoms and the last one assessing the patient's behavior during the interview.

The evaluations were carried out in both groups (control and intervention group) before discharge (after completion of the informed consent) and three months after the neurological event.

Timeline and data collection

Hospital discharge planning

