The following analysis model was followed: to study the differences that may exist between one group and another, before and after the intervention, a repeated measures ANOVA was carried out; to check how some variables influence others, a multivariate analysis was carried out and, finally, to know the mean and normal distribution of the variables, descriptive statistics were performed. An intragroup analysis was included by performing paired T-test studies along with Wilcolxon for non-parametric measurements. The program used for data analysis was JAMOVI (version 2.3.26).

Difficulties and limitations of the study

Regarding the limitations of this study, it is worth highlighting the biases possibly derived from the adherence to treatment of the users and their caregivers, as well as the behavior and involvement of the family member in the process that will likely induce differences in the results. It is worth highlighting the importance of the word of the patient and the caregiver due to the telephone process of the intervention, since it can lead to differences in the instructions provided by the occupational therapist and, therefore, in the treatment and final result.

Furthermore, an important limitation is the heterogeneity of the sample, since we are generally talking about patients who have had a stroke of any location, extent and volume. The random distribution of patients may result in the two groups having significant differences in the severity of their injuries or their potential for recovery. Also due to the heterogeneity of each patient's rehabilitation process, it is understood that, of the total sample size, certain patients will subsequently receive a greater number of conventional rehabilitation sessions than others, and some patients will probably not even receive any sessions. This is why it seems

interesting to subsequently study the care received by each user three months after discharge, as well as their level of functionality and quality of life.

Ethical considerations

During data collection, the anonymity of users was guaranteed. Participants will be informed of the intervention and will be asked to sign an informed consent, with participation being voluntary and allowing the user to abandon whenever they wish.

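### The mRS is compared between arms only by repeated measures ANOVA; a baseline-adjusted ordinal re-analysis would be easier to interpret and, if the shift is similar across grades, more powerful

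*Combined protocol and SAP*

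**What the plan says.** All references are to the combined protocol and SAP.

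- **Scale.** The section on assessments used in the study says of the mRS: "The scale ranges from 0 to 6, from perfect health with no symptoms to death".
- **Role.** The table of results and evaluations lists the mRS with the Barthel Index and SIS-16 under functional independence. Specific Objectives makes that domain secondary ("Secondary results: Functional independence and support needs in activities of daily living"). The primary is SAQOL-39 ("Primary outcome: Quality of life").
- **Timing.** Both arms are assessed "before discharge (after completion of the informed consent) and three months after the neurological event", so a baseline mRS is available.
- **Between-arm method.** Results analysis plan: "to study the differences that may exist between one group and another, before and after the intervention, a repeated measures ANOVA was carried out". No outcome is treated differently.
- **Other methods.** The rank method is for within-arm use: "An intragroup analysis was included by performing paired T-test studies along with Wilcolxon for non-parametric measurements". There is also a general statement, "to check how some variables influence others, a multivariate analysis was carried out", which names no model, outcome or covariate and is not presented as the treatment comparison.

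The plan gives no ordinal model, no baseline-adjusted treatment comparison and no rule for how a death enters the mRS analysis.

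**The concern.** The authors allow for measures that need non-parametric handling, but only within arms, where randomisation plays no part. The randomised comparison of an ordered seven-grade scale is left to a method that averages grade numbers.

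Two things follow. First, the reported effect is a difference in mean Rankin points. It counts a move from 5 to 6 (death) the same as a move from 0 to 1, and it is hard to translate into a statement about patients. Second, with only two visits the ANOVA interaction works on change scores, which is an inefficient way to use a baseline value that is already in the data set. With 60 patients, a loss of power on a secondary measure can decide whether a real shift is seen.

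**Working it through.** **1. The plan's own figure.** Sample selection and size gives "significance level of 5%, a power of 80% and a critical difference of 0.54, obtaining a sample of 30 participants per group", with SD 0.75. For two means, two-sided 5% (sidedness is not stated), n per arm = 2 × (1.960 + 0.842)² × 0.75² / 0.54² = 2 × 7.849 × 0.5625 / 0.2916 = 30.28. This rounds up to 31, against a stated 30. The figure reproduces closely, but it concerns SAQOL-39. The documents give no distribution, correlation or effect for the mRS, so all mRS inputs below are assumptions.

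**2. What the ANOVA tests.** Let D = 3-month mRS minus baseline mRS. With two visits, the group-by-time F equals the square of the two-sample t on D. The plan does not say which ANOVA term is the treatment test. I take the interaction, which is the favourable reading: in simulations at odds ratio 2.5, the group main effect had only 21–37% power.

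**3. Why change scores cost power.** If the variance σ² is equal at both visits and the correlation is ρ, the residual variance is 2σ²(1 − ρ) for change scores and σ²(1 − ρ²) after adjustment for baseline. The ratio, adjusted to change, is (1 + ρ)/2: 0.65, 0.75 and 0.85 at ρ = 0.3, 0.5 and 0.7. This part of the loss has nothing to do with the scale being ordinal.

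**4. Power under a common odds ratio of 3.** The simulation used 30 per arm, 3,000 trials per cell and latent baseline to 3-month correlation 0.3/0.5/0.7. Assumed baseline probabilities for mRS 0–5 were .02/.10/.20/.28/.32/.08. At 3 months, for mRS 0–6, the disabled mix was .10/.22/.24/.22/.14/.03/.05 and the mild mix .25/.32/.20/.12/.06/.02/.03.

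| Power, % (ρ = 0.3/0.5/0.7) | Disabled mix | Mild mix |
|---|---|---|
| Change-score ANOVA | 55/65/81 | 44/54/68 |
| Linear ANCOVA | 66/72/84 | 58/64/73 |
| Quade rank ANCOVA | 68/74/86 | 63/72/83 |
| Total gain, Quade − ANOVA | 13/9/5 | 19/18/15 |
| from baseline adjustment (ANCOVA − ANOVA) | 11/7/3 | 14/10/5 |
| from ordinal handling (Quade − ANCOVA) | 2/2/2 | 5/8/10 |

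A repeat with 4,000 trials per cell gave Quade against ANOVA of 68/75/85 against 54/66/81 (disabled) and 66/72/83 against 45/55/68 (mild), a gain of 4 to 21 points. At odds ratio 2 the total gain fell to about 3–11 points. Across these runs, ordinal handling contributed about 1–4 points (disabled) and 4–10 (mild).

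**5. A second set of assumptions.** This used three other distributions (0%, 3% and 10% deaths), latent correlation 0.3–0.85, odds ratio 2.5, and a proportional-odds model adjusted for baseline. Over the 12 scenarios, power was 42–89% for the ANOVA interaction and 56–91% for the ordinal model, a gain of about 2–14 points. ANCOVA reached 54–88%, so ordinal handling itself gave about 2–4.

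**6. When the shift is not similar across grades.**
- Benefit only at grade 4 or worse: proportional odds 27–50%, ANOVA 36–64%.
- Benefit only in grades 3–6 (ρ = 0.3/0.5/0.7), mild mix: Quade 8/9/10%, ANOVA 13/15/20%.
- The same, disabled mix: Quade 39/44/52%, ANOVA 36/45/58%. Quade trailed linear ANCOVA in all six cells, by 8–13 points.

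**7. Type I error at nominal 5%.** ANOVA interaction 3.7–5.0% in the second set and about 5% in the first; Quade 4.4–5.4%; proportional-odds likelihood-ratio test 5.2–6.5% in the second set, and 6–8% in a smaller 600-trial check.

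**The case against.** The strongest case for leaving the plan alone is this. The mRS is one of three instruments for a secondary domain. The ANOVA does not inflate false positives. The power advantage was shown under a common odds ratio, which is the condition that favours ordinal methods. Much of the gain comes from baseline adjustment, a separate matter that applies to every scale in the plan. And the analysis is already described as done.

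Most of that stands, and it rules out several stronger readings that a reader might infer:

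- *That the ANOVA is invalid.* It is not: it held its level in every null scenario. The weakness is in the estimate and in efficiency.
- *That an ordinal analysis is always more powerful on the same data.* It is not (step 6), and the documents give nothing from which to tell which pattern of effect applies.
- *That equal-step scoring causes the whole loss.* In the disabled mix, baseline adjustment accounts for most of it, especially at low correlation.
- *That ordinal methods weight death properly.* Ranks and proportional odds treat death simply as the next grade. Entry requires discharge home and excludes patients expected to live less than a year, so few deaths are likely by three months.
- *That the main conclusion or the sample size is affected.* Both rest on SAQOL-39.

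What the objection does not remove is the estimate. A mean difference in Rankin points assumes equal steps whatever the power. Nor does it explain why a baseline value collected in every patient should be used in its less efficient form. Functional independence is also the stated general objective, so the mRS result will be read.

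**Conclusion.** The point holds as a recommended improvement to a secondary analysis. The between-arm mRS comparison keeps its type I error, but it reports a quantity that assumes equal steps and makes inefficient use of baseline.

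If the shift is broadly similar across grades, a baseline-adjusted ordinal analysis at 30 per arm gains about 3–11 points of power at odds ratio 2 and 4–21 points at odds ratio 3. Roughly 1–4 of those points (disabled mix) or 4–10 (mild mix) come from ordinal handling, and the rest from baseline adjustment. If benefit is confined to the severe grades, power can be lost instead.

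These sizes rest on assumed mRS distributions, correlations and odds ratios, and on reading the ANOVA treatment test as the group-by-time interaction. The case on interpretation rests on none of these assumptions except the last.

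**What to change.** Time planning says the project ended in November 2022, and Results analysis plan is written in the past tense. So the change should be a re-analysis, labelled as such and reported beside the ANOVA, not a silent replacement:

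1. Analyse 3-month mRS with death scored 6, adjusted for baseline mRS.
2. Report a common odds ratio with 95% CI from proportional-odds regression on arm and baseline mRS.
3. State that inference rests on one p-value, from the baseline-adjusted Quade rank test. It holds its level at 60 patients, where the proportional-odds likelihood-ratio test can be slightly liberal. Say beforehand that the interval is descriptive if the two disagree.
4. Add linear ANCOVA on 3-month mRS as a check that does not assume proportional odds.
5. For the ANOVA itself, name the group-by-time interaction as the treatment test.

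The cost is a few sentences and minutes of analysis, with no new data. The downside is that the odds ratio assumes a similar shift across grades, and power is lost if the effect lies only at the severe end.

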Therefore, two groups were formed: an intervention group of 30 patients who will receive the early Occupational Therapy program in addition to the rehabilitation that they would receive independently of this study, and a control group of 30 patients who will receive the conventional rehabilitation.

Eligible patients were assigned to EOTIPS or the control group according to a pre-established computer randomized designation in blocks of six.

Inclusion and exclusion criteria

All patients must have diagnostic confirmation of stroke with single or multiple vascular lesions that had occurred in the same time period, demonstrated by neuroimaging tests (CT or MRI), be over 18 years of age, go home on discharge and live within a maximum of 30 minutes away from the hospital center, with >2 or <26 points on the National Institute of Health scale (NIHSS), 30–100 points on the Barthel Index (BI) on the second day after the stroke (with BI 100, the patient

can be included if the Montreal Cognitive Assessment is <26) and having been referred to the rehabilitation service as an outpatient. Inclusion in the study occurs prior to hospital discharge, within a two- week interval after the stroke.

Exclusion criteria are: NIHSS > 26, BI < 30, and life expectancy < 1 year. Also excluded are people with a previous stroke, dementia or other types of diseases that cause dementia and other neurological, psychiatric or medical diseases (for example, severe epilepsy, traumatic brain injury, schizophrenia, COPD, severe or unstable heart disease, sleep apnea) concomitants that could alter cognitive function, presence of moderate or severe aphasia, people who do not understand Spanish or English, as well as patients who have been referred to the Physical Medicine and Rehabilitation Unit as inpatients to receive intensive rehabilitation or who are discharged to a care home.

The variables will take into account: age, sex, educational level, marital status, nationality, mother tongue, employment, vascular territory and lesion volume.

List of results and evaluations

Patient evaluations	
Quality of life	- SAQOL-39
Level of functional independence	- BI - mRS - SIS-16
Perceptual-cognitive skills	- MoCA
Sensory-motor skills	Fugl MeyerBergTime up & go
Communication skills	- CAL
Anxiety and/or depression levels	- Berg - Hamilton

Assessments to be used in the study (all translated into Spanish)

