The rehabilitation and neurology departments were responsible for referring patients to the occupational therapist and including them in the study. Before starting rehabilitation, the occupational therapist and her family explored the patient's needs and desires and decide individual goals for the intervention period.

Occupational Therapy intervention during the discharge process. The intervention has a person-centered approach that is based on who the user is: their context, their history, their family members, their individual strengths and weaknesses. Individualized objectives will be established, taking into account the patient's potential and limitations. Examples of goals could be: being able to wash independently, hanging clothes or riding the bus, or how to manage bills. OT intervention may involve training in different activities or thinking about different ways to adapt to difficult situations to achieve a goal. For example, for some patients the intervention may consist of carrying out

ADLs in which they have a limitation with the support of the occupational therapist with the aim of enhancing their sense of security during its performance. Data will be collected through note taking and analyzed with qualitative content analysis.

The designed OT intervention includes:

- Prior to discharge: Initial evaluation and a hospital session.
- Post-discharge: A two-hour home visit, telephone follow-up, a one-hour visit one month after discharge and final evaluation three months later.

This early OT intervention will be carried out independently of the usual care of the rehabilitation service of the Torremolinos Maritime Hospital.

Time planning

The project will begin in January 2021 and was estimated to last one year and three months (estimated completion in March 2022). Finally, the project was completed on November 2022.

Day 1: Hospital (1 hour)					
Initial interview and evaluation.					
Day 2: Hospital (1 hour)					
Information about stroke. Postural care.					
Day 3: Home (2 hours)					
Environment assessment, equipment and					
recommendations and establishment of					
individualized objectives.					
Day 4 - day 29: PHONE FOLLOW-UP.					
Implementation of the rehabilitation by the patient					
and caregiver (individual objectives).					
Day 30: Home (1 hours).					
Final assessment of individualized objectives at					
home.					
After 3 months: Home (1 hour)					
Final evaluation.					

Results analysis plan

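### Both SAQOL-39 time points are written as contacts of the OT programme, and the plan does not say who assesses, whether they are masked, or whether baseline precedes allocation

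*Combined protocol and SAP*

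**What the plan says.** Under Timeline and data collection, the subsection on the OT intervention during the discharge process lists what the designed intervention contains. The pre-discharge entry is "Prior to discharge: Initial evaluation and a hospital session". The post-discharge entry is a home visit followed by "telephone follow-up, a one-hour visit one month after discharge and final evaluation three months later". The timetable under Time planning repeats this. Day 1, in hospital, is "Initial interview and evaluation", and the last row is a one-hour home contact after three months for the final evaluation.

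The section on assessments to be used gives the timing in these words: "carried out in both groups (control and intervention group) before discharge (after completion of the informed consent) and three months after the neurological event". It does not say who did the assessing. It describes the Beck inventory as self-administered but gives no mode of completion for SAQOL-39.

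On allocation, Sample selection and size says: "Eligible patients were assigned to EOTIPS or the control group according to a pre-established computer randomized designation in blocks of six". It does not place this step relative to the baseline evaluation, and it describes neither concealment nor masking. Under Hospital discharge planning, the rehabilitation and neurology departments were "responsible for referring patients to the occupational therapist and including them in the study". No other assessor is mentioned.

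The primary outcome is quality of life, and the sample size is based on SAQOL-39. The Results analysis plan compares the groups before and after the intervention by repeated measures ANOVA. The limitations section covers adherence, family involvement, telephone instructions and heterogeneity, but not assessment by someone aware of the allocation.

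**The concern.** A quality-of-life score can move with what the respondent expects and with who is asking. If baseline is taken once the arm is known, it may already reflect the allocation. By three months, intervention patients have had individual goal setting, two home visits and telephone follow-up. If the final SAQOL-39 is then collected at another contact of that programme, they answer within a relationship that controls do not have. The planned comparison rests on the two measurements, so a shift at either one that is not matched in the other arm becomes part of the estimated effect. A larger sample would not remove it. At stake is whether a positive SAQOL-39 result could be separated from the way the score was obtained.

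**Working it through.** **Text side by side**

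| Question | Programme description and timetable | Assessments section | Sample selection and size |
|---|---|---|---|
| Where is baseline placed? | Inside the programme, Day 1 | Both groups, before discharge, after consent | Not stated |
| Does baseline precede allocation? | Not stated | Not stated | Not stated |
| Where is the three-month evaluation placed? | Inside the programme, home contact | Both groups, three months after the event | Not stated |
| Who assesses? | Not stated; only the occupational therapist is named | Not stated | Not stated |
| Masking? | Not stated | Not stated | Not stated |

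The order consent, allocation, Day 1 evaluation fits every section. So does consent, evaluation, allocation, Day 2 hospital session. The text does not exclude the first.

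**The plan's own figure**

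Inputs from Sample selection and size: SD 0.75, difference 0.54, significance level 5%, power 80%, 30 per group. Sidedness is not stated.

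n per group = 2 × [0.75 × (1.960 + 0.842) / 0.54]² = 30.28, which agrees with the stated 30 apart from rounding. A one-sided test would need only 24, so the plan fits a two-sided test.

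**Illustration of what a net shift would do**

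Assumptions not in the documents: no true effect; a net shift b in the between-group comparison of 0.1 or 0.2; SD 0.75 for the analysed quantity.

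SE = 0.75 × √(2/30) = 0.194

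- b = 0.1 (0.1/0.54 = 19% of the planned difference): b/SE = 0.516. Two-sided error = P(Z > 1.444) + P(Z < −2.476) = 0.081.
- b = 0.2 (37%): b/SE = 1.033. Two-sided error = P(Z > 0.927) + P(Z < −2.993) = 0.178.

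The noncentral t distribution with 58 degrees of freedom gives 8.0% and 17.4%.

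**Same check on the change score**

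The SD of change is 0.75 × √[2(1 − ρ)], where ρ is the pre-post correlation. The plan does not give ρ, so a range is shown (noncentral t):

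| Assumed ρ | SD of change | Error, net shift 0.1 | Error, net shift 0.2 |
|---|---|---|---|
| 0.3 | 0.887 | 7.1% | 13.8% |
| 0.5 | 0.750 | 8.0% | 17.4% |
| 0.7 | 0.581 | 10.1% | 25.9% |

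A net shift of 0.2 can be 0.2 at three months alone, or −0.1 at baseline and +0.1 at three months. An equal shift at both times gives a net shift of zero.

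**The case against.** The case on the other side is that the text shows less than it may seem to. Four stronger readings are tempting, and the documents support none of them.

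- **Baseline was taken after allocation.** A reader might infer this from the Day 1 entry. But Day 1 contains only an interview and evaluation; information about stroke and postural care begin on Day 2. Allocation between the two would fit the text. The order is unstated.
- **The treating therapist administers SAQOL-39.** This is plausible because no one else is named, but it is not written. The programme description does not name SAQOL-39, and eleven instruments sit uneasily in a one-hour slot.
- **Any bias acts only in the intervention arm.** The same evaluations are required in both groups, patients are referred to the occupational therapist without distinction by arm, and controls who know their allocation may also shift their answers.
- **The bias must favour the intervention.** Equal shifts at both time points cancel in the before/after comparison, and an upward shift at baseline alone would work against the intervention.

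Two further objections also stand. The error rates rest on assumed shifts and are not evidence that bias occurred. And procedural changes come too late for a project that Time planning reports as finished in November 2022.

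None of this supplies the missing safeguard. Both evaluations are listed inside the programme, and the document describes no masked or separate assessor and no rule placing baseline before allocation.

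**Conclusion.** The concern holds as a gap in the plan, not as a demonstrated bias. The plan permits baseline to follow allocation and permits the three-month SAQOL-39 to be collected within the treatment relationship. The three-month part is the stronger, because the final evaluation is listed after the programme's home and telephone contacts. The baseline part depends on an order that is not given.

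Only a shift that differs between arms or between time points matters, and the documents give neither its size nor its direction. Under the assumptions of no true effect, 30 per group and SD 0.75 for the analysed quantity, a net shift of 0.1 or 0.2 would raise the two-sided 5% error to about 8% or 18%. On the change score the ranges are 7.1% to 10.1% and 13.8% to 25.9% for assumed correlations of 0.3 to 0.7. These figures show sensitivity; they do not estimate this trial's error rate.

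**What to change.** 1. **Baseline.** Take the initial evaluation out of the OT programme. In both arms, complete and lock all baseline instruments after consent and before the allocation is opened. This reorders existing steps and needs no extra staff.
2. **Three months.** Take the final evaluation out of the OT programme. Collect SAQOL-39 in the same way and setting in both arms, completed by the patient before any therapist contact where the patient is able, with any help recorded. Excluding dementia and moderate or severe aphasia makes this realistic for many patients. It will not suit all, since a Barthel Index as low as 30 is eligible. The cost is some blank or assisted items. The measure is partial: it does not remove patient expectation, and it does not protect observer-rated secondary outcomes such as Fugl-Meyer and Berg.
3. **This trial's report.** Items 1 and 2 can now serve only further use of the protocol. The report should state who assessed each arm, whether they were masked, and whether baseline preceded allocation. If assessors were not masked, or baseline followed allocation, this belongs in the limitations, and a positive SAQOL-39 result should be interpreted accordingly. The cost is a few sentences.
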